4.4.2 Non-hematological toxicity

4.4.2.1 The dose of SGI-110 will be reduced by one level for grade 3-4 reversible toxicities attributable to the drug independent of the disease status at the

- time of ongoing treatment with study drug. If toxicity is still present on next cycle with one dose level reduction, dose will be reduced with one more level again (minimum dose is 20 mg/m2 given for 3 subsequent days). If toxicity is present after 2 dose level reductions, SGI-110 will be discontinued.
- 4.4.2.2 Dose reduction for grade 2 reversible toxicities and other dose modifications can be implemented if in the best interest of the patient, after discussion with the primary investigator.
- 4.4.2.3 Infections are not considered drug related toxicity.
- 4.4.3 Patients with uncontrolled GVHD will not be eligible to receive SGI-110. If GVHD resolves, patients may receive SGI-110 with at least one level dose reduction in the subsequent cycle. If GVHD remains controlled, full dose can be used in the subsequent cycles.
- 4.4.4 Treatment delays up to 70 days (cohort #2 and #3) are allowed. For cohort #1, treatment delays will be decided by the treating physician or principal investigator based on the tolerability of the drug taken the best interest of the patient into account).
- 4.4.5 SGI-110 dose levels allowed in the study
 - 20 mg/m2 SC, Days 1 through 3 (dose level -3)
 - 20 mg/m2 SC, Days 1 through 5 (dose level -2)
 - 30 mg/m2 SC, Days 1 through 5 (dose level -1)
 - 40 mg/m2 SC, Days 1 through 5 (dose level 1)
 - 50 mg/m2 SC, Days 1 through 5 (dose level 2)
 - 60 mg/m2 SC, Days 1 through 5 (dose level 3)
- 4.5 Criteria to receive SGI-110
 - 4.5.1 Criteria to receive the first cycle
 - 4.5.1.1 Serum creatinine </= 1.5 mg/dL or creatinine clearance greater than 40 cc/min as defined by the Cockcroft-Gault Equation.
 - 4.5.1.1.1 Males (mL/min):(140-age)*IBW(kg) / 72*(serum creatinine(mg/dl))
 - 4.5.1.1.2 Females (mL/min):0.85*(140-age)*IBW(kg) / 72*(serum creatinine(mg/dl)).
 - 4.5.1.2 Serum bilirubin </= 1.5 x upper limit of normal (ULN)
 - 4.5.1.3 Aspartate transaminase (AST) or alanine transaminase (ALT) </= 2.5 x ULN
 - 4.5.1.4 Alkaline phosphatase </= 2.5 x UL
 - 4.5.1.5 No active bleeding.
 - 4.5.1.6 No uncontrolled GVHD.
 - 4.5.1.7 No clinical evidence of life-threatening infection.
 - 4.5.1.8 Negative serum or urine pregnancy test for females of childbearing potential. The only subjects who will be exempt from this criterion are postmenopausal women (defined as women who have been amenorrheic for > 12 months) or subjects who have been surgically sterilized or otherwise proven sterile.

- 4.5.2 Criteria to receive SGI-110 given as maintenance therapy (first cycle of maintenance therapy and beyond for cohorts 1 and 2 and second cycle and beyond for cohort 3). Each cycle is to be started 28-56 days after the previous cycle.
 - 4.5.2.1 ANC >/=1.0 x 10⁹ /L without daily growth factor (Intermittent use of growth factor is allowed as clinically indicated and platelet count>=50 X 10⁹/L with or without transfusion
 - 4.5.2.2 No clinical evidence of life-threatening infection.
 - 4.5.2.3 No active bleeding.
 - 4.5.2.4 No active uncontrolled GVHD.
 - 4.5.2.5 Serum creatinine < 2 mg/dL.
 - 4.5.2.6 Serum bilirubin < 1.5 mg/dL.
 - 4.5.2.7 ALT </= 200 IU/ml unless related to patient's malignancy.
 - 4.5.2.8 Negative serum or urine pregnancy test for females of childbearing potential. The only subjects who will be exempt from this criterion are postmenopausal women (defined as women who have been amenorrheic for > 12 months) or subjects who have been surgically sterilized or otherwise proven sterile.
- 4.6 Donor Lymphocyte Infusion (for cohorts 1 and 2)
 - 4.6.1 The patients will receive 3 planned DLI infusions after enrollment to the study if below criteria is met.
 - 4.6.1.1 No active bleeding.
 - 4.6.1.2 No uncontrolled GVHD.
 - 4.6.1.3 Patients should be off concurrent of use systemic immune suppressive other than calcineurin inhibitors and sirolimus.
 - 4.6.1.4 No clinical evidence of life-threatening infection
 - 4.6.1.5 No evidence of autologous reconstitution of the hematopoiesis.

 Chimerism studies from peripheral blood and/or bone marrow at study entry or at later time points on study will be used to rule out autologous.
 - 4.6.2. Patients will not receive DLI:
 - 4.6.2.1. If criteria summarized under 4.6.1 is not met.
 - 4.6.2.2 Donor is not available
 - 4.6.2.3. The treating physician and the PI think it is in the best interest of the patient not to receive DLI.
 - 4.6.3 For patients eligible to receive the DLI, the first DLI is planned to be given on the 6th day of the second SGI-110 cycle immediately after the completion of the 5 days of SGI-110 administration if no GVHD observed. If the 6th day falls over a weekend day or holiday, the DLI will be given on the very first week day following the 6th day.
 - 4.6.4 Additional DLI will be permitted in patients without uncontrolled GVHD on the 6th day of the 4th and 6th course of SGI-110 at the discretion of the treating physician. If the 6th day falls over a weekend day or holiday, the DLI will be given on the very first week day following the 6th day.
 - 4.6.5 DLI dose:
 - 4.6.5.1 CD3 1 x 10⁷/kg for matched related donor; 3 x 10⁶/kg for matched unrelated and mismatched unrelated donors.
 - 4.6.5.2 There will be no scheduled dose escalations and CD3+ cells dose of DLI

can be lower at the discretion of the treating physician on subsequent administrations.

- 4.6.6 Criteria to give DLI
 - 4.6.6.1 No active bleeding.
 - 4.6.6.2 No uncontrolled GVHD.
 - 4.6.6.3 Patients should be off concurrent of use systemic immune suppressive other than calcineurin inhibitors and sirolimus.
 - 4.6.6.4 No clinical evidence of life-threatening infection
 - 4.6.6.5 No evidence of autologous reconstitution of the hematopoiesis.

 Chimerism studies from peripheral blood and/or bone marrow at study entry or at later time points on study will be used to rule out autologous reconstitution.

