RICAZA study Investigators conducted a study using subcutaneous azacitidine in 27 AML patients who had undergone reduced-intensity conditioning (RIC) allogeneic stem cell transplantation (19). The conditioning regimen was fludarabine, melphalan, and alemtuzumab, and the azacitidine regimen consisted of 36 mg/m2 for 5 consecutive days every 28 days for up to 10 cycles. The median time to start of azacitidine treatment was 64 days after the allogeneic stem cell transplantation. An additional 19 patients enrolled as the control group, received the same conditioning regimen, but no maintenance therapy. The investigators found that 3 of the 27 patients who received maintenance therapy developed grade 2 acute GVHD, and none developed grade 3e4 GVHD. Two patients developed limited chronic GVHD of the skin, and none developed chronic extensive GVHD. In comparison, the control group had a higher GVHD rate, with 7 of 19 developing grade 2 acute GVHD and 7 of 19 chronic GVHD. Despite these encouraging results, 7 of the 27 patients relapsed at a median of 6 months after transplantation.

Decitabine is another epigenetic therapy that has been investigated in the post-transplant maintenance setting (20). The maximum tolerated dose (MTD) was defined as the maximum dose at which $\leq 25\%$ of people experience dose-limiting toxicities during the first cycle of treatment. Twenty-four patients were enrolled and 22 were evaluable. All 4 dose levels were completed and no MTD was reached. Overall, decitabine maintenance was well tolerated. Grade 3 and 4 hematological toxicities were experienced by 75% of patients, including all patients treated at the highest dose level. Nine patients completed all 8 cycles and 8 of them remain in CR. Nine patients died from relapse (n = 4), infectious complications (n = 3), and GVHD (n = 2). Most occurrences of acute GVHD were mild and resolved without interruption of treatment; 1 patient died of acute gut GVHD. In conclusion, decitabine maintenance is associated with acceptable toxicities when given in the post-allo transplantation setting.

Despite the encouraging results reported, pre-emptive strategies, to prevent relapse, including pharmacological, immunological and cellular therapies pose the dilemma of administering potentially toxic therapy without evidence of relapse. Therefore patient selection for the right group of patients to be included in those studies is very important.

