Starting at 36 mg/m2 daily and 60 mg/m2 weekly (44 AML, and 7 MDS patients), clinical responses were observed: 2 CRs, 1 CRp, and 1 CRi in heavily pretreated AML patients; 1 mCR and 1 HI in MDS patients previously treated with azacitidine. All responses were in patients who achieved >10% LINE-1 hypomethylation. The most common adverse events (AEs), regardless of relationship to SGI-110, were diarrhea (21%), febrile neutropenia (17%), fatique/injection site pain/nausea at 15% each. The most common drug-related AEs were injection site pain (15%), fatigue (8%), nausea (6%), and thrombocytopenia (5%). The MTD was not reached with the weekly regimen up to 125 mg/m2 weekly x 3. With the daily regimen, 125 mg/m2 daily x 5 resulted in 2 dose-limiting toxicities (DLTs) of febrile neutropenia in 3 MDS patients (1 associated with bacteremia, and the other with sepsis and thrombocytopenia Grade 4) while none of the 9 patients with AML had DLT at that dose (14). Since the abstract publication, maximum hypomethylation was noted at the 60 mg/m2 dose, while clinical MTD was defined at 90 mg/m2 dose. Therefore the Phase II study proceeded to compare 60 versus 90 mg/m2 daily for 5 days in newly diagnosed MDS and AML. A further arm investigated SGI-110 60 mg/m2 daily x 10 days in AML salvage. Finally SGI-110 60 mg/m2 daily x 5 is being evaluated in patients with MDS and progression on azacitidine/decitabine therapy.

The Phase II randomized study of the biologic effective dose 60 mg/m2 daily x 5 and clinical Phase II dose 90 mg/m2 daily x 5 is ongoing. As of June 30, 2013, sixty-seven patients (50 relapsed/refractory AML, 17 treatment naïve elderly AML) were treated and had a minimum follow up of 3 months. Patients were randomized to either 60 mg/m² dose (32 patients) or 90 mg/m² dose (35 patients). The median age was 66 years (range, 22–84), 69% were male, and ECOG PS of 0/1/2 was reported in 11/47/9 patients respectively. Median number of prior regimens was 2 (range, 0–10). Patients' characteristics were well balanced between the 2 dose groups. The primary endpoint of overall remissions (CR, CRp, or CRi) was observed in 17/67 patients (25% with 95% CI, 16–37%). There were 8 complete remissions (CR, CRp, or CRi) in 50 patients with relapsed/refractory AML (16% with 95% CI, 7-29%); and 9 complete remissions

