2.5 Risks of SGI-110 Based on Early Clinical Data

For the most up-to-date clinical safety information, please refer to the most recent Investigators' Brochure.

The most common risks of SGI-110 are similar to decitabine. These include myelosuppression (neutropenia, febrile neutropenia, thrombocytopenia, and anemia) and its consequences such as fever, infection, sepsis, bacteremia, or bleeding. While in GLP toxicity studies with SGI-110 subcutaneous injections, no adverse local site reactions were noted in the multiple-dose rat and rabbit studies, clinical data indicate injection site pain, irritation, or inflammation in approximately 15% of patients. Local pain seems to be ameliorated by the use of ice packs before or after injection, injecting SGI-110 slowly instead of a push, and carefully avoiding intradermal injections.

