- 4.2.1.11 Treatment with SGI-110 will be stopped at any time point if patients exhibit evidence of treatment failure, disease progression, experience of unacceptable toxicity, or the investigator determines that the discontinuation of treatment is in the patient's best interest as provided in Section 6.0.
- 4.2.2. Cohort 2: Patients without morphological evidence of relapse but with minimal residual disease.
 - 4.2.2.1 The enrolled patients will start treatment at the dose level 1 which is 40 mg/m2 SC daily, days 1 to 5. Treatment delays up to 70 days are allowed.
 - 4.2.2.2 The response assessments schedule will be as follows:
 - 4.2.2.2.1 The first response assessment will be performed after the second cycle of SGI-110 given prior to initiation of third cycle.
 - 4.2.2.2.2 For patients who have persistency of detectable MRD after the second cycle of SGI-110 and continue to receive SGI-110 the next assessment will be performed after the fourth cycle.
 - 4.2.2.3 For patients who have persistency of detectable MRD after the fourth cycle of SGI-110 and continue to receive SGI-110 the next assessment will be performed after the sixth cycle.
 - 4.2.2.2.4 Patients may have an earlier disease assessment rather than the indicated time point in the study protocol at the discretion of the treating physician and principal investigator.
 - 4.2.2.3 If patients still have detectable MRD even after the fourth cycle of SGI-110, further treatment (maximum two more cycles) with SGI-110 will be given only if the patient, treating physician and principal investigator determine such an action as the best interest of the patient.
 - 4.2.2.4 Patients who are documented to have no detectable MRD at any time point while treated with SGI-110 will continue the study drug as maintenance therapy at subsequent cycles after documentation of MRD negative status.
 - 4.2.2.5 The dose level of SGI-110 can be increased at least one dose level at the discretion of treating physician and principal investigator if persistency of MRD is documented at any time point of disease assessment while on study.
 - 4.2.2.6 For patients with detectable minimal residual disease at study entry, treatment with SGI-110 will be continued until treatment failure or for a

- maximum of 12 cycles if they have become negative for minimal residual disease at any time point within the first 6 cycles of study drug.

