- 4.2.2.7 Treatment with SGI-110 will be stopped at any time point if patients exhibit evidence of treatment failure, disease progression, experience of unacceptable toxicity, or the investigator determines that the discontinuation of treatment is in the patient's best interest as provided in Section 6.0.
- 4.2.3. Cohort 3: High risk AML and MDS patients who are in complete remission morphologically with no evidence of minimal residual disease by flow cytometry or cytogenetic or molecular testing after allogeneic stem cell transplantation.
 - 4.2.3.1 The enrolled patients will start treatment at the dose level -1 which is 30 mg/m2 SC daily, days 1 to 5 for each 28-day treatment cycle.
 - 4.2.3.2 Treatment delays up to 70 days will be allowed.
 - 4.2.3.3 The response assessments will be performed per departmental guidelines which is day +100, 6th month, 1- year after allogeneic stem cell transplantation.
 - 4.2.3.4 Disease assessment can be done at any time point after transplantation if it is deemed indicated by the treating physician and/or principal investigator.
 - 4.2.3.5 The dose level of SGI-110 can be increased at least one dose level at the discretion of treating physician and principal investigator if deemed in the best interest of the patient by the treating physician and/or principal investigator.
 - 4.2.3.6 For patients who remain in remission without detectable minimal residual disease at study entry, treatment with SGI-110 will be continued until treatment failure or for a maximum of 12 cycles.
 - 4.2.3.7 Treatment with SGI-110 will be stopped at any time point if patients exhibit evidence of treatment failure, disease progression, experience of unacceptable toxicity, or the treating physician and/or principal investigator determines that the discontinuation of treatment is in the patient's best interest as provided in Section 6.0.
- 4.2.4 **Cross-over.** Patients treated on cohort #2 (patients with minimal residual disease while in morphological remission and cohort #3 (maintenance treatment cohort) will be allowed to receive higher doses of SGI-110 if they progress while on therapy with the study drug. Patients who are considered for cross-over to another study cohort due to progression of disease with an aim to receive higher doses of SGI-110 will be screened for the eligibility of that study cohort prior to initiation of higher doses of study drug.
- 4.3 SGI-110 Reconstitution and Administration

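### Section 4.4.2.3 says without limit that infections are not drug-related toxicity; read as an attribution rule, it conflicts with 2.5 and 8.2.3 and would under-count related infections in the safety endpoint

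*Combined protocol and SAP*

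**What the plan says.** Section 4.4 governs dose modification. Under non-hematological toxicity, 4.4.2.1 sets a mandatory rule: "The dose of SGI-110 will be reduced by one level for grade 3-4 reversible toxicities attributable to the drug". Section 4.4.2.2 allows discretionary changes for grade 2 events and other reasons. Section 4.4.2.3 then says, as a complete item: "Infections are not considered drug related toxicity". It carries no qualifier of grade, neutropenia, timing or purpose.

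Elsewhere the protocol treats infection as a risk of the drug. Section 2.5 names myelosuppression and "its consequences such as fever, infection, sepsis, bacteremia, or bleeding" among the most common risks of SGI-110. Section 2.4 reports that, in phase I, 125 mg/m2 daily for five days "resulted in 2 dose-limiting toxicities (DLTs) of febrile neutropenia in 3 MDS patients (1 associated with bacteremia, and the other with sepsis and thrombocytopenia", the thrombocytopenia being grade 4. That dose is above the 60 mg/m2 maximum in 4.4.5.

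The safety rules are in Section 8:
- 8.1 makes the investigator or designee responsible for attribution of all AEs, and confines the AE page of the eCRF to related AEs and SAEs.
- 8.2.1 includes a table of recommended AE recording by attribution, grade and trial phase.
- 8.2.3 requires the investigator to classify each AE or SAE as suspected or not suspected, against written definitions and with no exception for infections.
- 8.3 requires all SAEs to be reported whatever their relationship, from consent to 30 days after the last dose. After that, 8.3 and 8.5 require reports only of events suspected of being, or found to be, related.

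The relationship of AEs to SGI-110 is part of secondary endpoint 1.3.2.1.

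**The concern.** Section 4.4.2.3 is worded as a statement about causality. It does not say that infections leave the dose unchanged; it says they are not drug related. Staff therefore have two written instructions on whether an infection can be attributed to SGI-110, and no text says which governs.

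The label has consequences in this protocol. It enters the safety endpoint directly, and it decides whether some events are recorded or reported at all. Infection is an expected harm of a myelosuppressive drug after transplant, including in cohort 3, whose patients are in remission without detectable residual disease. Each cohort is single-arm, so no comparison group would reveal a shortfall in related infections.

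**Working it through.** No arithmetic applies: the plan gives no figure on this point. The check sets the sections side by side and follows an infection through the rules.

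**1. Section 4.4.2.3 against 2.5.** One section lists infection, sepsis and bacteremia as consequences of the drug's myelosuppression. The other says infections are not related to the drug. Taken literally, both cannot hold for an infection that follows drug-induced neutropenia.

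**2. Section 4.4.2.3 against 8.2.3.** Section 8.2.3 asks for an event-by-event judgement. A rule that fixes the answer for a whole class of events leaves nothing to judge. Neither section refers to the other.

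**3. Consequences if 4.4.2.3 is applied to attribution.** Every infection would then be labelled not suspected. I take that label to correspond to the unrelated or unlikely rows of the table in 8.2.1. The table is damaged in the available text, but both rows appear to recommend recording in phase II from grade 3 upwards and not below.

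| Infection | Governing text | Effect of the literal reading |
|---|---|---|
| Non-serious, grade 1-2, up to 30 days after last dose | 8.1; table in 8.2.1 | Not recorded under either |
| Non-serious, grade 3 or higher, same window | 8.1 against the table | Not recorded under 8.1; apparently recorded under the table |
| Serious, up to 30 days after last dose | 8.3 | Recorded and reported; only the relationship label changes |
| Serious, more than 30 days after last dose | 8.3, 8.5 | Not reportable, because reporting then requires relatedness |

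The second row shows a further inconsistency. The restriction in 8.1 and the recommendation in the table disagree about unrelated grade 3-5 non-serious events, whatever 4.4.2.3 means. If the table is followed, the recording loss falls mainly on grade 1-2 non-serious infections.

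**4. Direction.** The literal reading can only move infections from related to unrelated, so any error lowers the related count. If practice differs between staff, the same infection is classified in different ways.

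**5. Primary endpoints and stopping rules.** Response in cohorts 1 and 2 is remission or resolution of MRD within six cycles. Section 7.1 counts stopping for severe toxicity before remission as failure, but a patient who stops without remission is a non-responder whatever the cause is called. The cohort 3 endpoint is time to progression or death. None of these depends on attribution of an infection.

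**The case against.** The strongest reply is placement. The sentence sits under dose modifications, two items after a rule that turns on attribution to the drug, so its natural role is to limit that rule. Section 8 has its own causality process, which neither mentions 4.4.2.3 nor exempts infections. It can also be said that 2.5 describes a consequence of hematologic toxicity, handled in 4.4.1, while 4.4.2.3 concerns non-hematologic toxicity, so the two can coexist. The phase I events were febrile neutropenia with associated infection, at about twice this trial's maximum dose.

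Much of this stands. A dosing-only intent is likely, and whether infection should change the dose is the sponsor's choice. The harm arises only if the sentence is used for attribution. But the limit is not written, and the sentence uses the language of attribution.

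Three stronger readings are tempting, and the documents do not support them:

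- *A reader might infer that serious infections disappear from the safety data.* Up to 30 days after the last dose they do not: 8.3 captures them whatever the label, and any infection that is fatal, life-threatening or needs admission is an SAE under 8.2.1.
- *A reader might infer that patients with serious infection must continue at an unchanged dose.* Section 4.4.2.2 allows discretionary changes, and the stop rules include unacceptable toxicity and a judgement that stopping serves the patient; in 4.2.3.7 treatment stops if the treating physician or "principal investigator determines that the discontinuation of treatment is in the patient's best interest". That ground needs no attribution to the drug.
- *A reader might size the problem from the decitabine maintenance trial in Section 2.0, where* "Nine patients died from relapse (n = 4), infectious complications (n = 3), and GVHD (n = 2"). Those deaths are not attributed to the drug and their timing is not given. Fatal infections are also the events that 8.3 protects best. The count says nothing about how many infections would be mislabelled here.

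**Conclusion.** The point holds as a conflict of wording with a conditional effect. Section 4.4.2.3, read literally, gives a causality rule that disagrees with 2.5 and pre-empts 8.2.3. If it is used for attribution, related infections are under-counted in 1.3.2.1, some non-serious infections go unrecorded, and serious infections more than 30 days after the last dose fall outside SAE reporting. The documents do not show that anyone would use it so.

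The size cannot be derived: the documents give neither an expected number of infections nor a share that investigators would call related. The direction is clear, and the effect is confined to a secondary safety endpoint and to safety reporting. The conclusion on grade 3-5 non-serious events rests on my reading of a damaged table. This is a cheap improvement worth making; it does not threaten the trial's main conclusions.

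**What to change.** Reword 4.4.2.3 along these lines: *For the purpose of 4.4.2.1 only, infections do not trigger mandatory dose reduction; causality of every infection is assessed under 8.2.3.* If dosing was always the intent, this only states it.

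Align 8.1 with the recording table in 8.2.1, so that all grade 3-5 infections are recorded and tabulated whatever their attribution. This also resolves the disagreement between 8.1 and the table for these events.

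The cost is a short amendment to each section, some extra AE entry, and possibly higher reported rates of related toxicity. Dosing rules, sample size and the primary analyses are unchanged.

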4.4.1 Hematologic Toxicity

4.4.1.1 Cohort 1:

- 4.4.1.1.1 No dose reductions, delays or modifications are required for hematologic toxicities during the treatment cycles given with an intent to achieve CR/CRi. It is assumed that low counts observed in the presence of active disease (no morphological remission) are due to involvement by the disease and require treatment for improvement. Patients will not require dose modifications for hematological toxicity before they are reported to achieve morphological remission.
- 4.4.1.1.2 For patients who achieve complete morphological remission (CR/CRi) on study, they will receive the subsequent cycles (given as maintenance therapy) approximately every 28 days, provided that their peripheral blood counts have recovered (ANC>=1.0 X 10⁹ /L and platelet count>=50 X 10⁹/L)). If the peripheral count recovery is delayed beyond 42 days from Day 1 of the prior cycle and the delay is presumed to be secondary to therapy (after confirmation of achieving morphological remission), the SGI-110 doses may be reduced at least by one level for subsequent doses (e.g. from 40 to 30 mg).

4.4.1.2 Cohort 2:

- 4.4.1.2.1 No dose reductions, delays or modifications are required for hematologic toxicities during the treatment cycles given in the continuous presence of MRD. It is assumed that low counts in the presence of MRD are due to disease involvement and require treatment for improvement. Indeed, the dose level of SGI-110 can be increased at least one dose level at the discretion of treating physician and principal investigator if persistency of MRD is documented at any time point of disease assessment while on study independent of hematological toxicities observed as indicated at 4.2.2.4.
- 4.4.1.2.2 After the documentation of MRD negative status with the SGI-110 treatment, if the peripheral count recovery is delayed beyond 42 days from Day 1 of the prior cycle and the delay is presumed to be secondary to therapy, the SGI-110 doses may be reduced at least by one level for subsequent doses (e.g., from 30 to 20 mg).
- 4.4.1.3 Cohort 3: If the peripheral count recovery is delayed beyond 42 days from Day 1 of the prior cycle and the delay is presumed to be secondary to therapy, the SGI-110 doses may be reduced at least by one level for subsequent doses (e.g., from 30 to 20 mg).

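### Section 4.5 gives no start-of-cycle criteria for pre-response cycles 2-6 in cohorts 1 and 2, and the maintenance ALT limit is printed in a unit that cannot bind

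*Combined protocol and SAP*

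**What the plan says.** Section 4.5.1 is headed "Criteria to receive the first cycle". It bars treatment for active bleeding, uncontrolled GVHD, life-threatening infection or a positive pregnancy test. It also sets organ limits, among them "Serum creatinine </= 1.5 mg/dL or creatinine clearance greater than 40 cc/min", bilirubin up to 1.5 x ULN, and AST or ALT up to 2.5 x ULN.

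Section 4.5.2 applies to maintenance, that is "first cycle of maintenance therapy and beyond for cohorts 1 and 2 and second cycle and beyond for cohort 3". It repeats the infection, bleeding, GVHD and pregnancy conditions, adds blood-count thresholds, and sets different organ limits: "Serum creatinine < 2 mg/dL", bilirubin below 1.5 mg/dL, and "ALT </= 200 IU/ml unless related to" the malignancy.

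Cohorts 1 and 2 may receive up to six cycles before response (4.2.1.4 to 4.2.1.6; 4.2.2.3). The first scheduled response assessment follows cycle 2 (4.2.1.2.1; 4.2.2.2.1), although an earlier one is allowed.

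On blood counts before response, 4.4.1.1.1 says for cohort 1: "No dose reductions, delays or modifications are required for hematologic toxicities during the treatment cycles given with an intent to achieve CR/CRi". Section 4.4.1.2.1 says the same for cohort 2 while MRD persists. Section 4.4.2.3 states: "Infections are not considered drug related toxicity".

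**The concern.** The protocol sets a bar for infection, bleeding, pregnancy and organ function at cycle 1 and sets one again in maintenance. Between the two, while disease or MRD is still present, no list applies. That interval includes the second 60 mg/m2 cycle in cohort 1, which is the highest dose level allowed. Blood-count thresholds are waived in these cycles, and section 2.5 names infection, sepsis, bacteremia and bleeding among the consequences of the drug's myelosuppression.

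The first DLI is planned for day 6 of cycle 2 (4.6.3). Active bleeding or life-threatening infection bars that infusion (4.6.1, 4.6.6), but no written rule holds the five SGI-110 doses just before it for the same conditions.

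The ALT limit in 4.5.2.7 is a separate matter. It is an operative dosing threshold, and as printed it has no effect. What is at stake in both parts is consistent, documented dosing safety.

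**Working it through.** **1. Which list covers which cycle**

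| Cycle | Cohorts 1 and 2 | Cohort 3 |
|---|---|---|
| 1 | 4.5.1 | 4.5.1 |
| 2-6, before response | none | not applicable |
| Maintenance | 4.5.2 | 4.5.2, from cycle 2 |

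**2. What other sections supply for the uncovered cycles**

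- GVHD: 4.4.3 applies at any cycle, "Patients with uncontrolled GVHD will not be eligible to receive SGI-110". Covered.
- Drug-attributable grade 3-4 reversible toxicity: 4.4.2.1 requires dose reduction, and discontinuation if it persists after two reductions. Covered, except that 4.4.2.3 takes infection out.
- Unacceptable toxicity: 4.2.1.11 and 4.2.2.7 require stopping.
- Delay: permitted by 4.2.1.1, 4.4.4 and 7.1 (up to 56 days for toxicity), without naming a condition that requires it.
- Cycles 5-6: need the agreement of patient, treating physician and principal investigator (4.2.1.4, 4.2.2.3).
- Tests: 5.1.1 schedules creatinine, bilirubin, SGPT (ALT) and a pregnancy test within 72 hours of each cycle, with no limit or action attached.

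No written hold remains for life-threatening infection, active bleeding, a positive pregnancy test, or organ dysfunction not attributed to the drug. Given the agreement step at cycles 5-6, this matters mainly at cycles 2-4.

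**3. How many second cycles are uncovered**

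Inputs from 7.1, per cohort: stop at 8 patients with 0 responses, stop at 20 with at most 1, maximum 25. With true response rate p:

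- P(stop at 8) = (1-p)^8
- P(stop at 20) = 8p(1-p)^7 x (1-p)^12, that is, one response in the first 8 and none in the next 12
- E[N] = 8 x P(stop at 8) + 20 x P(stop at 20) + 25 x P(neither)

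| p | Stop at 8 | Stop at 20 | Stop early | Table 1 of 7.1 | E[N] | Two cohorts |
|---|---|---|---|---|---|---|
| .05 | .663 | .151 | .81 | .82 | 13.0 | 25.9 |
| .10 | .430 | .108 | .54 | .54 | 17.1 | 34.3 |
| .15 | .272 | .055 | .33 | .32 | 20.1 | 40.2 |
| .20 | .168 | .023 | .19 | .18 | 22.0 | 44.1 |

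The exact early-stopping probabilities agree with the plan's table to within .01. If each patient starts cycle 2 without an earlier documented response, the expected number of uncovered second cycles is about 26 to 44. The maximum is 25 x 2 = 50.

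**4. ALT unit**

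200 IU/ml x 1000 ml/L = 200,000 IU/L, which is 1000 times 200 IU/L. The documents give no ULN. Assuming 35 to 55 IU/L, the printed limit is about 3,600 to 5,700 x ULN. Read as 200 IU/L, it is about 3.6 to 5.7 x ULN, a plausible clinical limit.

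**5. Do the existing organ limits nest?**

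They do not, for creatinine (Cockcroft-Gault formula as in 4.5.1.1.1):

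- Man aged 40, IBW 75 kg, creatinine 2.2 mg/dL: (140-40) x 75 / (72 x 2.2) = 47.3 mL/min. He passes 4.5.1.1 and fails 4.5.2.5.
- Man aged 65, IBW 65 kg, creatinine 1.9 mg/dL: (140-65) x 65 / (72 x 1.9) = 35.6 mL/min. He fails 4.5.1.1 and passes 4.5.2.5.

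Copying either list into the gap would therefore create an inconsistency with the other.

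**The case against.** The strongest reply is that looser rules before response are a stated strategy, and that written controls already narrow the gap. Cohort 1 delays are left to the clinicians, low counts are treated through, unacceptable toxicity must lead to stopping, and cycles 5-6 need three-party agreement. Absence of life-threatening infection or active bleeding is itself a clinical judgement, so writing it down documents the decision more than it changes it. The pregnancy and laboratory tests are already scheduled.

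Much of this stands, and it limits the point to a residual gap. It does not close that gap: the waiver with a stated rationale concerns blood counts only, and nothing explains why infection, bleeding and pregnancy are written conditions before and after these cycles but not during them.

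On organ limits the objection also has force. Importing the cycle-1 values would hold the second man above while he has active disease, although 4.5.2.5 would allow him treatment in remission.

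The ALT unit is fairly called a clerical error, which many clinicians would read as IU/L. It adds no weight to the first part, but a dosing threshold should be correct as printed.

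**Conclusion.** Both parts hold, at the level of a change that should be made. The gap is a missing written hold for four conditions in pre-response cycles 2-6 of cohorts 1 and 2, mainly cycles 2-4. Its reach is about 26 to 44 expected second cycles, 50 at most. This assumes that every patient starts cycle 2 and that none has response documented earlier; cross-over patients are not counted. The documents give no rate of infection, bleeding, pregnancy or organ dysfunction in these cycles, so no harm can be quantified.

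Three stronger readings are not supported:

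- A reader might infer that the protocol permits or requires dosing a patient with sepsis or a positive pregnancy test. It does not: delay and stopping remain available. Section 4.2.1.8 restricts taking a cohort 1 patient off therapy in the first four courses; it does not restrict holding a cycle.
- A reader might multiply 50 patients by all five cycles from 2 to 6. That total would need every patient to remain without documented response through six cycles, and it overlooks the agreement step at cycles 5-6.
- A reader might expect an effect on the response endpoint or the stopping rules. There is none.

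That 4.5.2.7 was meant to read IU/L is an inference and needs confirming.

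**What to change.** 1. Correct 4.5.2.7 to 200 IU/L, after the sponsor confirms the intended unit.
2. Add to 4.5 a short list for pre-response cycles 2-6 in cohorts 1 and 2: no clinical sign of life-threatening infection, no active bleeding, and a negative pregnancy test with the exemptions of 4.5.1.8. State that the blood-count waiver of 4.4.1.1.1 and 4.4.1.2.1 still applies, and leave GVHD to 4.4.3.
3. Optional organ limits: if the sponsor wants them, make them no stricter than either existing list. That means creatinine below 2 mg/dL or clearance above 40 cc/min; bilirubin at the looser of 1.5 x ULN and 1.5 mg/dL; ALT at the looser of 2.5 x ULN and 200 IU/L (200 IU/L is the looser whenever the ULN is below 200 / 2.5 = 80 IU/L). Include an exception for abnormality related to the malignancy.

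The cost is protocol wording. No test is added: 5.1.1 already schedules the pregnancy test, creatinine, bilirubin and ALT around each cycle. AST and alkaline phosphatase are not on that schedule, so they are left out. The downside is an occasional held cycle and, in cohort 2, loss of study treatment if the next cycle cannot be given within 70 days of the preceding one (8.4).
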